1.2 OBJECTIVE AND ENDPOINTS

Table 2 - Objectives and endpoints

	Objectives	Endpoints
Primary	
 The primary objective of Part B is to evaluate the long-term safety and tolerability of BIVV009 in patients with primary CAD 	
Safety Endpoints:
 
 Incidence of treatment-emergent adverse events (TEAEs) and serious adverse events (SAEs) Change from baseline in clinical laboratory evaluations Change from baseline in systemic lupus erythematosus (SLE) panel Change from baseline in vital signs Change from baseline in electrocardiograms (ECG) data Physical examination findings Incidence of infections of \geq Grade 3 severity (ie, requiring intravenous [IV] antibiotics) Serum disease-related biomarkers Incidence of hemolytic breakthrough through EOT Incidence of thromboembolic events
Secondary	
 The secondary objective of Part B is to investigate the durability of response during long-term treatment with BIVV009 in patients with primary CAD. 	
The following parameters of disease activity will be assessed:
 
 Hemoglobin Bilirubin QOL assessments (FACIT-Fatigue, EQ-5D-5L, SF-12, PGIS, and PGIC) LDH Transfusion requirements Haptoglobin Total healthcare resource utilization at EOT
Tertiary/exploratory	
 To describe the safety and patient satisfaction with the convenience of home infusions with BIVV009 in a subset of patients To describe the safety of undiluted infusions with BIVV009 To evaluate the immunogenicity of BIVV009 	
For subjects receiving home infusions:
 
 Satisfaction with home infusion after first home infusion and after fourth home infusion Incidence of AEs with onset within 24 hours of a home infusion 
For subjects receiving undiluted infusions:
 
 Incidence of AEs with onset within 24 hours of an undiluted infusion Anti-drug antibodies

Objectives	Endpoints

• Pharmacokinetics of BIVV009	
• Plasma concentrations of BIVV009• PK parameters: Appropriate exposure parameters (C_{max}, AUC) will be derived using a population PK approach

• Pharmacodynamics of BIVV009	
• Weislab-CP• CH50• Total C4• C1q• C1s

1.2.1 Estimands

There are no primary efficacy endpoints in Part B. Thus, estimands will not be utilized in this SAP.

2 SAMPLE SIZE DETERMINATION

Patients in Part B will be a subset of the patients enrolled in Part A. All patients who complete Part A, including those receiving transfusions, will be eligible for Part B. Patients who withdraw from the study in Part A, including those who received prohibited concomitant medications, will not be eligible to participate in Part B. Subject inclusion and exclusion criteria for Part A can be found in Sections 5.1 and 5.2 of the protocol.

No power and sample size analysis was conducted for Part B. Patients from Part A were enrolled into Part B following Part A EOT. The power and sample size calculation for Part A can be found in the Part A SAP.

3 ANALYSIS POPULATIONS

The important protocol deviations defined in Part A do not apply to Part B; and thus, the Per-Protocol Population described in the protocol was determined to have little utility and has not been included in this SAP.

The following populations for analyses are defined:

Table 3 - Populations for analyses

Population	Description
Full Analysis Set	All subjects who enroll into Part B and receive at least 1 dose (including partial dose) of study drug. The Full Analysis Set is synonymous with the Intent-to-Treat Population described in the protocol.
Safety Analysis Set	All subjects who receive at least 1 dose (including partial dose) of study drug in Part B. Note that the Safety Analysis Set is the same as the Full Analysis Set in this study.
PK Analysis Set	All subjects who receive at least 1 dose of study drug in Part B and have evaluable PK concentrations.
PD Analysis Set	All subjects who receive at least 1 dose of study drug in Part B and have at least 1 evaluable PD sample.

4 STATISTICAL ANALYSES

Part B is an open-label study with no blinding or randomization. No formal statistical hypotheses will be tested. Analyses of efficacy endpoints will be primarily descriptive.

Statistical analysis will be performed by Sanofi, using SAS 9.4 or higher and, where appropriate, additional validated software.

4.1 GENERAL CONSIDERATIONS

Safety, efficacy, and PK/PD data will be summarized using standard summary statistics for continuous, categorical, and time-to-event data. Data will be summarized for the populations defined.

No statistical hypothesis testing is planned.

Continuous Variables

Continuous variables will be summarized using descriptive statistics including the number of non-missing values (n), mean, standard deviation (SD), median, minimum and maximum. Where specified in the table shells, the 25th and 75th percentiles will also be provided. Means, medians, and the 25th and 75th percentiles will be presented to one decimal place beyond that with which the data were captured. SDs will be presented to two decimal places beyond that with which the data were captured. Minimum and maximum will be displayed to the same number of decimal places as that with which the data were captured.

Unless impractical within a given table, statistics will be aligned by the decimal place (or assumed decimal place) in the summary tables.

Categorical Variables

Categorical variables will be summarized by counts and percentages. All percentages will be rounded to one decimal place. The percentage will be suppressed when the count is zero. Unless specified otherwise, the denominator for all percentages will be the number of subjects with non-missing data for a given summarization.

Part B Study Treatment Period

For subjects who enroll into Part B, the Part A study treatment period starts at the date of first study drug administration and ends at the date of Week 26 visit. The Part B study treatment period starts following completion of Part A (ie, immediately following Week 26 visit) and ends at the ET/EOS/Safety follow-up visit, which is 9 weeks after each subject's last dose.

Combined Study Period

The Combined Study Period includes all visits in Part A and Part B and will be utilized for a subset of analyses in order to support regulatory submissions and/or publications.

Thromboembolic Events

Thromboembolic events prior to Part A study entry are recorded as medical history in the eCRFs, while thromboembolic events on Part A and Part B study are captured as adverse events. Both medical history and adverse events will be coded according to Medical Dictionary for Regulatory Activities (MedDRA) v23.0 or higher.

All thromboembolic events reported (as AEs) will be reviewed and determined by internal medical staff via medical adjudication.

Hemolytic Breakthrough

Hemolytic breakthrough at any visit is defined as

- A decrease of 2 g/dL or more in Hgb from the last scheduled visit, and
- One of the followings:
 - An increase of LDH from the last scheduled visit, or
 - An increase of bilirubin from the last scheduled visit, or
 - A decrease in haptoglobin from the last scheduled visit.

4.2 PARTICIPANT DISPOSITIONS

Subject disposition will be summarized for all enrolled subjects in Part B by treatment arm in Part A (ie, BIVV009 and Placebo) and Total. Subject disposition will be summarized including the number of subjects in FAS, Safety Analysis Set, PK Analysis Set, and PD Analysis Set. The number of subjects with the status of completed Part B and discontinued Part B early, including the primary reason for those who discontinued, will be tabulated for all subjects enrolled in Part B.

Protocol deviations

All protocol deviations will be recorded throughout the study. Major and minor protocol deviations/violations are to be pre-specified prior to database lock. All major protocol deviations will be summarized for FAS by treatment arm in Part A (ie, BIVV009 and Placebo) and Total.

4.3 PRIMARY ENDPOINT(S) ANALYSIS

The primary objective of Part B is to evaluate the long-term safety and tolerability of BIVV009 in patients with primary CAD. Thus, all endpoints related to this objective and the analyses for these endpoints will be described, in full, in [Section 4.7](#).

4.4 SECONDARY ENDPOINT(S) ANALYSIS

Unless specified otherwise, all analyses described will be performed using the FAS. All summaries of efficacy endpoints will be descriptive and will not test any formal hypotheses. All summaries will be tabulated by treatment arm in Part A (ie, BIVV009 and Placebo) and Total.

4.4.1 Key/Confirmatory secondary endpoint(s)

4.4.1.1 Definition of endpoint(s)

Continuous endpoints

The continuous endpoints are:

- Mean change from baseline in hemolytic parameters including
 - Hemoglobin
 - Total bilirubin
 - LDH
 - Haptoglobin
- Mean change from baseline in FACIT-Fatigue score
- Mean change from baseline in QOL, as assessed by the change in the five-level EQ-5D-5L scores by visit
- Mean change from baseline in QOL, as assessed by the change in the 12-item short form survey (SF-12[®])
- Number of transfusions and total transfusion units
- Annualized number of transfusions and annualized transfusion units

Categorical Endpoints

The categorical endpoints include:

- Incidence of thromboembolic events
- Incidence of hemolytic breakthrough
- PGIC
- Change from baseline in PGIS

4.4.1.2 Main analytical approach

Continuous Endpoints

The continuous endpoints will be summarized by visit and treatment arm using descriptive statistics for the FAS according to [Section 4.1](#). Change from baseline will also be summarized by visit.

Line plots of hemoglobin, bilirubin, and FACIT-F score over time, starting at Baseline/Day 0, will be presented. Additionally, line plots of mean change from baseline in hemoglobin, bilirubin, and FACIT-F score over time, starting at Baseline/Day 0, will be presented.

The endpoints related to transfusions and transfusion units will be summarized by study period using the FAS.

Annualized values will be calculated for each patient using the following formula:

$$\text{Annualized value} = \frac{\text{Number of events during the Study Period}}{\text{Total number of days during the Study Period}} \times 365.25$$

Response (Categorical) Endpoints

The categorical endpoints will be summarized descriptively by visit and treatment arm for the using the FAS according to [Section 4.1](#) with the exception of total healthcare resource utilization at EOT (Part A), which will be presented in a listing.

All thromboembolic events reported (in Adverse Events) will be reviewed and determined by internal medical staff along with investigators. In case that there are discrepancies between the medical review and investigators' assessment, separate analyses will be carried out for both sets of events. Date of event occurrences will be verified. The incidence of thromboembolic events and hemolytic breakthrough events will be summarized using all data in Part B (including data from the Week 79 visit and beyond).

4.4.1.3 Details on endpoints based on patient-reported outcomes (PROs)

The patient-reported outcome (PRO) endpoints are as follows:

- Continuous Endpoints
 - FACIT-Fatigue score
 - EQ-5D index score
 - EQ-5D-5L visual analogue scale
 - SF-12 physical component score (PCS) and mental component score (MCS)
 - SF-12 sub-scale scores
- Categorical Endpoints
 - Patient's Global Impression of Change (PGIC)
 - Patient's Global Impression of [Fatigue] Severity (PGIS)
 - EQ-5D-5L Descriptive System

Details of the above PRO instruments and algorithms for deriving the scores can be found in the Part A SAP.

When applicable missing items will be handled based on the specific PRO instrument. Subjects missing baseline evaluations would not be included in the PRO analyses.

Healthcare Resource Utilization

The number of healthcare visits by type (office visit, hospital ER visit, hospitalization, and ICU stay) will be collected and presented in a listing.

4.5 TERTIARY/EXPLORATORY ENDPOINT(S) ANALYSIS

4.5.1 Definition of endpoint(s)

Per the protocol, home infusions will be performed at pre-selected countries/sites for a select number of subject who meet the criteria specified in Appendix K of the protocol. For these subjects, a survey will be conducted after the first and fourth home infusion to assess patient satisfaction with the home infusion.

4.5.2 Main analytical approach

The patient satisfaction survey will be summarized descriptively for the subset of subjects who receive home infusions.

4.6 MULTIPLICITY ISSUES

There are no multiplicity issues for Cadenza Part B.

4.7 SAFETY ANALYSES

All safety analyses will be performed on the Safety Analysis Set, stratified by dose cohort, unless otherwise specified, using the following common rules:

- The analysis of the safety variables will be essentially descriptive, and no testing is planned.
- Safety data in participants who do not belong to the safety population (eg, exposed but not randomized) will be provided.

4.7.1 Extent of exposure

The extent of IMP exposure will be assessed by the duration of IMP exposure and treatment compliance and summarized for the Safety Analysis Set. Per the protocol, subjects rolling over to Part B are to receive a loading dose (in a blinded manner). For analysis of Part B exposure, this loading dose will be included in the Part B database. Thus, Part B exposure will start on the date/time of the Week 26 loading dose.

Duration of IMP exposure

Study drug exposure, measured by the duration of study treatment, the number of BIVV009 administrations and total actual BIVV009 dose, will be summarized by study period for the Safety Analysis Set by treatment cohort in Part A (ie, BIVV009 and Placebo) and Total.

The duration of the study treatment (in weeks) is calculated as follows:

1. Combined Study Period: (date of last dose – date of first dose in Part A + 15)/7
2. Part B Study Period: (date of last dose – Part B start date + 15)/7

Treatment compliance

Study drug compliance for a subject is measured by the percent of number of doses received out of the number of protocol-specified doses. The proportion of subjects whose compliance is less than 80%, 80% - <100%, and $\geq 100\%$ will also be summarized. In addition, the number of subjects and number of doses administered out of study windows and number of partial infusion doses will be summarized.

4.7.1.1 Overall exposure

The actual dose administered at each visit is calculated as:

$$\text{Total volume administered} / \text{Total volume prepared} * \text{assigned dose.}$$

The total BIVV009 dose will be summarized as follows:

1. Combined Study Period: The summation of all actual doses administered in Parts A and B.
2. Part B Study Period: The summation of all actual doses administered in Part B, alone.

The number of subjects with missing infusion due to COVID-19 will be presented.

4.7.2 Adverse events

General common rules for adverse events

AEs will be classified using the MedDRA system organ classes and preferred terms. MedDRA version 23.0 or higher will be used throughout the study.

In general, AEs will be analyzed based on *incidence*, defined as the proportion of subjects who had at least one occurrence of an event out of the number of subjects in the Safety Analysis Set.

All summary tables and listings will only include treatment-emergent adverse events in Part B unless noted otherwise.

Unless specified otherwise, system organ classes and preferred terms within each SOC will be presented alphabetically. For the purpose of summarization, a subject is counted once in a SOC or preferred term if the subject reported one or more events in that SOC or preferred term. Unless specified otherwise, percentages will be based on the number of subjects in the Safety Analysis Set.

Overall Summary of Adverse Events

An overall summary of TEAEs will be provided which tabulates the number and percentage of subjects who experienced a TEAE, related TEAE, treatment-emergent SAE, treatment-emergent related SAE, treatment-emergent Grade 3 or higher AE, treatment-emergent infections of Grade 3 or higher severity, TEAE thromboembolic event, TEAE autoimmune event, TEAE potential hypersensitivity event, and TEAEs within 24 hours after the start of infusion; TEAEs within 24 hours after the start of home infusion of BIVV009 and TEAEs within 24 hours after the start of undiluted infusion of BIVV009; the number and percentage of subjects who discontinued treatment and/or the study due to an AE; and the number and percentage of subjects who died. In addition, the number of TEAEs, TESAEs, TEAE thromboembolic events and TEAEs within 24 hours after the start of infusion will be presented.

Treatment-emergent Adverse Events

The incidence of TEAEs will be summarized by SOC and preferred term.

Adverse Events in Descending Order of Incidence

Tables will be provided which display TEAE and TESAE preferred terms in descending order of incidence. Only preferred terms will be included in these tables (ie, the display will not include SOCs).

A similar table will be provided for Grade 3 or higher TEAEs. AEs for which the assessment of severity is missing will be included in this table.

Severity of Adverse Events

AEs are classified by the Investigator for CTCAE grades v4.03. A summary of TEAEs by system organ class, preferred term, and CTCAE grade will be presented. AEs with a missing severity will be excluded from this table and listed separately to supplement the summary table. A subject will be counted once for each SOC and preferred term based on the greatest severity within that SOC and preferred term, respectively.

Relationship of Adverse Events to Study Drug

AEs are classified by the Investigator for relationship to study drug (“Not related,” “Possible,” and “Probable”). For summary tables, an AE with relationship of “Possible” or “Probable” will be considered “Related.” A summary of TEAEs by SOC, preferred term, and relationship (“Related” or “Not related”) will be presented. AEs with a missing relationship will be counted as “Related” in the summary table. A subject will be counted once for each SOC and preferred term based on the highest relationship within that SOC and preferred term, respectively.

Serious Adverse Events

Any AE reported as resulting in death, immediate risk of death (life threatening), inpatient hospitalization or prolongation of existing hospitalization, persistent or significant disability/incapacity, or a congenital/anomaly/birth defect will be classified as an SAE by the

Investigator. An SAE may also be any other medically important event that, in the opinion of the Investigator, may jeopardize the subject or may require intervention to prevent one of the other outcomes listed above.

Treatment-emergent SAEs and treatment-emergent related SAEs will be summarized by system organ class and preferred term. Treatment-emergent SAEs will also be summarized by preferred term in descending order of incidence.

Adverse Events Leading to Treatment Discontinuation and/or Study Withdrawal

AEs leading to treatment discontinuation and/or study withdrawal will be listed. All AEs reported on the AE log for the item “Action Taken with Study Drug” with a response of “Study drug permanently discontinued” or for the item “Was the subject terminated from this study due to this AE?” with a response of “Yes” will be included.

Death on Study

A listing of deaths occurring on study will be provided.

Analysis of adverse events of special interest (AESIs)

AEs within 24 Hours after the Start of Site Infusion

All AEs within 24 hours after the start of site infusion are captured in the eCRF. Incidence of AEs within 24 hours after the start of site infusion will be summarized by SOC and preferred term.

AEs within 24 Hours after the Start of Home Infusion

All AEs within 24 hours after the start of home infusion are captured in the eCRF. Incidence of AEs within 24 hours after the start of home infusion will be summarized by SOC and preferred term. AEs within 24 hours after the start of home infusion will be flagged on the listing of adverse events.

AEs within 24 Hours after the Start of Undiluted Infusion

All AEs within 24 hours after the start of undiluted infusion are captured in the eCRF. Incidence of AEs within 24 hours after the start of undiluted infusion will be summarized by SOC and preferred term. AEs within 24 hours after the start of undiluted infusion will be flagged in the listing of adverse events.

Infections and Infections of \geq Grade 3 Severity

Infections will be captured based on MedDRA SOC of “infections and infestations.” Incidence of infections of Grade 3 or higher will be summarized by preferred term. Listings of all infections, infections of Grade 3 or higher and serious infections will be provided.

Autoimmune Events

Treatment-emergent autoimmune events will be adjudicated and flagged on the Listing of adverse events.

Hypersensitivity Events

Treatment-emergent hypersensitivity events will be adjudicated and flagged on the Listing of adverse events.

Anti-drug Antibody

Subjects will be evaluated for anti-drug antibodies at Baseline and at the ET/EOS/Safety Follow-up visits in Part B. Subjects with negative or positive anti-drug antibodies at baseline and post baseline, as well as the incidence and prevalence will be summarized for the Combined Study Period by dose cohort in Part B (ie, 6.5 g and 7.5 g) and Total. A listing will be provided for subjects with negative or positive anti-drug antibodies along with the associated titer if available. If applicable, TEAEs for those subjects will be included in the same listing.

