At least 15 patients in Part B will be proposed to receive infusions with study drug undiluted with saline solution. Undiluted infusions may begin in patients who consent to and without evidence of intolerance of the study drug and who satisfy the following criteria:

1. Able to comprehend and give informed consent for receiving undiluted infusions of BIVV009 and willing to be infused for at least 1 dose
2. Treated for at least 3 months in Part B (completed visit Day 273)
3. No history of hypersensitivity reaction to BIVV009
4. Not selected to participate in home infusion administration
5. Considered by Investigator as suitable for undiluted infusion of BIVV009

Each qualified patient is supposed to receive at least one undiluted infusion of BIVV009, however, patients are free to continue with undiluted infusion of BIVV009 until the end of study. Undiluted infusions with BIVV009 versus infusions of BIVV009 diluted in saline will be captured through the case report form (CRF) for drug administration.

A safety follow-up visit for collection of AE data, PK, PD, and anti-drug antibody (ADA) samples will be performed 9 weeks after administration of the last dose of study drug in patients who discontinue early or following the end of dosing in the long-term extension period. Samples for PK, PD, and ADA will also be collected from patients who experience a hematological breakthrough event. The study will be complete 12 months following LPO for Part A at which time all patients receiving on-going treatment will proceed to an End-of-Study (EOS) visit.

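### The Part B SAP's default adverse-event denominator is not overridden for home and undiluted infusions, so applied literally it dilutes their rates with patients never exposed to that mode

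*SAP*

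**What the plan says.** Protocol section 3.5 gives Part B two relevant exploratory objectives: to describe the safety of home infusions and of undiluted infusions. Both modes go to subsets. Section 4.1 of the protocol plans at least 15 undiluted patients, and the minimum exposure is low: "Each qualified patient is supposed to receive at least one undiluted infusion of BIVV009". Home patients agree to at least 4 home doses (Appendix K). The two subsets exclude each other (section 2.2.4), and both require a completed Day 273 visit and no earlier hypersensitivity reaction.

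The Part B SAP then says:

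- Section 3 defines the Safety Analysis Set as "All subjects who receive at least 1 dose (including partial dose) of study drug in Part B". It defines no home or undiluted set.
- Section 4.7.2 says that AE incidence is, in general, "the proportion of subjects who had at least one occurrence of an event out of the number of subjects in the Safety Analysis Set". It adds the default: "Unless specified otherwise, percentages will be based on the number of subjects in the Safety Analysis Set".
- Further on in 4.7.2: "Incidence of AEs within 24 hours after the start of home infusion will be summarized by SOC and preferred term"; and "Incidence of AEs within 24 hours after the start of undiluted infusion will be summarized by SOC and preferred term". Neither sentence gives a denominator, nor do the home and undiluted rows of the overall summary of treatment-emergent AEs.
- Table 2 (section 1.2) places these two AE endpoints under headings that limit them to subjects receiving that mode.
- Section 4.5.2 limits the satisfaction survey explicitly. It is "summarized descriptively for the subset of subjects who receive home infusions".
- Section 4.7.1 summarises the number of administrations by study period, not by setting or dilution.

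**The concern.** The methods section uses a defined term, incidence, whose definition puts all Part B patients in the denominator. Only some of them receive a home or undiluted infusion. A programmer who follows 4.7.2 would divide events that can occur only in the subset by a number that includes patients never at risk of them. Where the SAP wanted a subset in its methods, for the satisfaction survey, it said so.

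A second weakness is that the measure is per subject. One undiluted infusion is enough to count, while patients dosed on site throughout are infused every 2 weeks for a year or more. The planned tables give no infusion counts by mode from which a reader could allow for this.

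These tables answer the two exploratory safety objectives. Protocol section 2.2.4 itself names more infusion-related reactions as a possible risk of the undiluted form, so an undiluted rate that is too low by construction would mislead on the question the tables are meant to inform.

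**Working it through.** The documents state no figure to reproduce: Part B has no sample-size calculation and no expected AE rate. The check therefore shows what the default rule does over a range of assumed sizes.

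**Inputs.** About 40 patients are to be randomised (protocol 4.1), which bounds N, the number dosed in Part B. The undiluted subset n is at least 15 (protocol 4.1). The home subset size is not stated. I assume N of 30 to 40.

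**1. Dilution.** With x affected patients, the rate among the exposed is x/n and the rate under the default is x/N. Reported rate = exposed rate × n/N; understatement = N/n.

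| Assumed n of N | n/N | Understatement |
|---|---|---|
| 15 of 40, undiluted | 0.375 | 2.7-fold |
| 15 of 35, undiluted | 0.43 | 2.3-fold |
| 15 of 30, undiluted | 0.50 | 2.0-fold |
| 20 of 30, undiluted | 0.67 | 1.5-fold |
| 10 of 40, home | 0.25 | 4.0-fold |
| 25 of 40, home | 0.625 | 1.6-fold |

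The last row is the largest possible home subset when N = 40 and 15 patients have undiluted infusions (40 − 15 = 25), because no patient may have both.

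**2. In percentages, for 15 of 40** (Clopper-Pearson 95% limits, for illustration; the SAP does not plan them in these tables):

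| Affected | Of 15 exposed | Of 40 |
|---|---|---|
| 0 | 0%, upper limit 21.8% | 0%, upper limit 8.8% |
| 1 | 6.7% (0.2 to 31.9) | 2.5% (0.1 to 13.2) |
| 3 | 20.0% (4.3 to 48.1) | 7.5% (1.6 to 20.4) |

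**3. Number of infusions.** Take the same risk r per infusion for every mode, independent between infusions. Per-subject incidence after k infusions is 1 − (1 − r)^k. With r = 1% assumed:

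- k = 1: 1.0%
- k = 4: 1 − 0.99^4 = 3.9%
- k = 13: 1 − 0.99^13 = 12.2%
- k = 26 (about one year of dosing every 2 weeks): 1 − 0.99^26 = 23.0%

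With r = 2% the values for k = 1, 4 and 26 are 2.0%, 7.8% and 40.9%. Modes with identical risk per infusion can thus show very different per-subject percentages. How different depends on how many infusions of each mode patients receive, which the plan does not tabulate.

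**The case against.** The strongest reply is that the SAP already specifies otherwise. Table 2 heads these endpoints for subjects receiving each mode, protocol section 4.3.5 does the same, the incidence definition applies only in general, and the default carries an exception. Section 4.1 also has a second general rule, under which "the denominator for all percentages will be the number of subjects with non-missing data for a given summarization", and it refers to table shells that are not in the documents and may settle the matter. This has force. A reader might infer that the SAP has fixed the whole set as denominator and that both objectives will be answered with understated risks; the documents do not establish that. But the Table 2 headings give no denominator, the endpoint beneath them is still the defined term incidence, and the AE-specific rule is the more specific of the two general ones. The text supports two readings that give different rates.

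A reader might also infer that the lack of a matched comparator understates risk. It does not. The objectives are descriptive, Part B plans no testing, and no claim of equal or better safety is planned. A site-infusion table exists, though it is not matched on patient, period or number of infusions; that limits comparison across modes without lowering the absolute rate. Nor do the documents show that the site category contains undiluted infusions. The SAP lists site, home and undiluted separately and does not define site, so the three may be exclusive. Since undiluted patients may not be home patients, the overlap is possible and needs a sentence.

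The consequences are also recoverable. Numerators are unaffected, home and undiluted events are flagged in the listing, and the CRF records setting and dilution. Patients may stay on undiluted infusions to the end of the study, so the one-infusion case is an extreme.

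**Conclusion.** The point holds as a gap in specification. Section 4.7.2 and the overall summary do not state the exposed-subset denominator for home and undiluted AEs, and the rule that fills the gap dilutes the percentages. For undiluted infusions the understatement runs from 1.5-fold to 2.7-fold over the assumed sizes; for home infusions it cannot be fixed, because the subset size is not given. If the Table 2 headings govern, there is no dilution, but the missing infusion counts by mode remain. The per-infusion illustration rests on an assumed common, independent risk and shows a limit on comparison, not a bias in the absolute rate. Because the text allows both readings, it should be settled before the tables are programmed.

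**What to change.** In Part B SAP section 4.7.2, and for the matching rows of the overall summary:

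1. State that the denominator for home-infusion AEs is subjects with at least one home infusion, and for undiluted-infusion AEs subjects with at least one undiluted infusion.
2. Report the number of infusions, and affected infusions per 100 infusions, separately for home, undiluted site and diluted site.
3. State that the site-infusion category excludes undiluted infusions.

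The same patients' diluted site infusions after Day 273 may be shown as descriptive context where they exist. This is optional: it is empty for a patient who switches to undiluted at the first opportunity and stays on it.

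No new data are needed, since the drug-administration CRF already captures setting and dilution (protocol section 4.1 and Appendix K). The cost is SAP wording, a little extra tabulation, and percentages for the new modes that will look less favourable than under the default.
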